**Endpoint Rationale:** 

The target engagement biomarkers, urinary MCP1/uCr and TIMP1/uCr, are the primary endpoints of this study as we hypothesize that the levels of this biomarkers at baseline reflect TNF up-regulation in the kidney and after TNF inhibition reflect target engagement. Neither eGFR nor urinary protein is a primary endpoint measure. However, we measure eGFR and urinary protein to provide estimates for future trials.

## 5. Study Methods

## 5.1 General Study Plan

This study is designed as a proof-of-concept multi-center, open-label single-arm clinical trial addressing the treatment of patients with FSGS or TR-MCD. Eligibility for the study is assessed during a 6-week screening period where bio-samples are used to assess TNF up-regulation and other laboratory and medical history criteria.

Patients are recruited from the active population of patients with FSGS or TR-MCD at participating sites. TR-MCD is defined as persistent proteinuria despite pre-trial immunomodulating treatment. Following informed consent and when appropriate, assent, a screening visit is conducted. Patients with elevated urinary TIMP1/uCr and MCP1/uCr levels and meeting all other eligibility criteria are scheduled to receive adalimumab every two weeks for 8 weeks (5 total doses).

A participant is considered to have completed the study if they complete the study through week 14 or if they withdraw prior to completion of the final study visit. Participants are followed in the study even if study medication is prematurely discontinued unless they withdraw their consent to do so. End of study is constituted by completion of the last visit for the final participant in the study protocol.

## 5.2 Inclusion-Exclusion Criteria and General Study Population

#### 5.2.1 Participant Inclusion Criteria

- 1. Kidney biopsy confirmed FSGS or MCD
- 2. For Minimal Change Disease patients only, history of resistance to corticosteroid therapy
- 3. Increased urinary excretion of biomarkers of TNF activation (urinary MCP1/uCr and/or urinary TIMP1/uCr) at study screening
- 4. eGFR>30 ml/min/1.73 m^2 at screening
- 5. Urine protein to creatinine ratio ≥1.5 g/g at screening
- 6. Age 6-80 years
- 7. Weight >15kg
- 8. Stable therapy with angiotensin converting enzyme inhibitors, angiotensin receptor blockers, and oral immunosuppression agents for at least 30 days prior to enrollment
- 9. Birth control use in females of child-bearing potential
- 10. Informed consent and assent if applicable

#### 5.2.2 Participant Exclusion Criteria

- 1. Kidney or other solid organ or bone marrow transplant recipient
- 2. Allergy or intolerance to investigational agent
- 3. Secondary FSGS
- 4. Severe obesity, i.e., BMI >40 kg/m^2
- 5. Live virus vaccine in the past 3 months
- 6. Malignancy, current or in the past 5 years
- 7. Active local or systemic bacterial, fungal or viral infection
- 8. Active or latent Hepatitis B, Hepatitis C, HIV, or tuberculosis defined as quantiferon test positive
- 9. History of demyelinating disease, e.g., Multiple Sclerosis or Guillain-Barre
- 10. History of heart failure
- 11. Active liver disease, defined as AST or ALT > 2.5x Upper Limit of Normal
- 12. Systemic lupus erythematosus or ANA > 1:80
- 13. History of inflammatory bowel disease, e.g., ulcerative colitis or Crohns disease
- 14. Cyclophosphamide in past 90 days, Rituximab in the past 180 days
- 15. Pregnancy or nursing
- 16. Blood white blood cell count <4,500/mm^3; Hg <9 g/dL; Platelet count <150,000/mm^3 at enrollment. Use of an erythropoiesis stimulating agent will not be an exclusion criterion.
- 17. Concurrent use of interleukin-1 antagonist (Anakinra), other TNF blocking agent, methotrexate or abatacept
- 18. Diabetic nephropathy

## 5.3 Randomization and Blinding

This is a single-arm study and thus randomization and masking are not possible to minimize bias.

## 5.4 Study Assessments

The Schedule of Activities details the study procedures:

	Screening	Week 0	Week 2	Week 8	Week 10	Week 14
Visit window	+/-2 DAYS	+/-4 DAYS				
Consent	Х					
Medical History	Х	Χ	Х	Χ	Х	Х
Archived Kidney Biopsy Report	Х					
Submission						
Archived Kidney Tissue sections						
submitted, if available*						
Concomitant Medications	X	Χ	Χ	Χ	Χ	X
Physical Exam	X	Χ	Χ	Χ	Χ	X**
Adverse Events Assessment		Χ	Х	X	Х	X
Vital Signs	X	Χ	Х	X	Х	X**
HRQOL assessment		Χ	Χ	Χ	Х	
Comprehensive Metabolic	Х	Х	Х	Х	Х	X**
Panel						

	Screening	Week 0	Week 2	Week 8	Week 10	Week 14
CBC with Platelets and	Х	Χ	Х	Х	Х	X**
Differential						
Urine Protein:Creatinine	Х	Χ	Х	Х	Х	X**
Assessment of Infections	Х					
MCP1/TIMP1 (spot urine)	Х	Χ	Х	Х	Х	
Pregnancy Test	Х	Χ	Χ	Χ		
Biorepository specimen	X*	Χ	Χ	Χ	Х	
Adalimumab dosing		Χ	Χ	Χ		

\* Do not submit if most recent biopsy specimen has already been submitted to NEPTUNE study; \*DNA collected at screening only

## 6. Outcomes

## 6.1 Primary Outcome Assessments

Spot urinary biospecimens to assay MCP1 (ng/mL), TIMP1 (ng/mL) and creatinine (mg/mL) are collected with spot urine tests at screening and weeks 0, 2, 8, and 10. Urine creatinine is used to normalize the urinary MCP1 and urinary TIMP1 by calculating the ratio of urinary MCP1 and urinary creatinine and the ratio of urinary TIMP1 and urinary creatinine.

Urinary MCP1 and Urinary TIMP1 are measured by ELISA methods [2]. There are no published reference ranges for the urinary MCP1/uCr nor urinary TIMP1/uCr levels; however, lower values for both biomarkers are associated with less intra-renal TNF activation. [1] Thus, either absolute or relative changes from baseline to post-treatment time points indicate TNF pathway target engagement by adalimumab and support the proof of concept of this trial.

#### 6.2 Secondary Outcome Assessments

## 6.2.1 Safety measures

An adverse event is any untoward medical occurrence in a clinical study participant administered a medicinal (investigational or non-investigational) product. Adverse events, whether serious or non-serious, related or not related, are recorded after administration of adalimumab (i.e., are treatment-emergent events) until week 14. All serious adverse events that do resolve by the end of the study, or that do not resolve upon discontinuation of the subject's participation in the study, are followed until any of the following occurred:

- The event resolves
- The event stabilizes
- The event returns to baseline, if a baseline value/status were available
- The event can be attributed to agents other than the study drug or to factors unrelated to study conduct
- It becomes unlikely that any additional information can be obtained (participant or health care practitioner refusal to provide additional information, or lost to follow-up after demonstration of due diligence with follow-up efforts).

\*\* Optional procedures required if study visit is conducted in-person

Adverse events are categorized by severity and by relationship to study medication by the site investigators, and by system organ class by the coordinating center investigators.

The status of edema is important in this patient population as a manifestation of disease, so any edema (over all body locations and by each location) over the course of the 10-week intervention period is evaluated within the adverse event reporting as new or worse than prior to study.

As a clinically significant change, any fever event (temperature ≥38.5°C) is recorded over the course of the 10-week intervention period.

#### 6.2.2 Laboratory abnormalities

For ALT, AST, and total bilirubin, the laboratory result value is abnormal when it is greater than 2 x upper limit of normal (ULN). Laboratory result values either below the age-matched lower limit of normal (LLN) or above the age-matched upper limit of normal is defined as laboratory abnormalities for hemoglobin, hematocrit, and platelet count. The age-matched normal ranges of ALT, AST, total bilirubin, hemoglobin, hematocrit, and platelet count are provided below:

	Age Group	Male	Female
ALT	> or =6 year	7-55 U/L	7-45 U/L
AST	6-13 years	8-60 U/L	8-50 U/L
	> or =14 years	8-48 U/L	8-43 U/L
Total bilirubin	6 to 17 years	0.0-1.0 mg/dL	0.0-1.0 mg/dL
Hemoglobin	6-8 years	11.5-14.3 g/dL	11.5-14.3 g/dL
	9-10 years	11.8-14.7 g/dL	11.8-14.7 g/dL
	11-14 years	12.4-15.7 g/dL	11.9-14.8 g/dL
	15-17 years	13.3-16.9 g/dL	11.9-14.8 g/dL
	Adults	13.2-16.6 g/dL	11.6-15.0 g/dL
Hematocrit	6-7 years	34-42%	34-42%
	8-11 years	35-43%	35-43%
	12-15 years	38-47%	35-43%
	16-17 years	40-50%	35-43%
	Adults	38.3-48.6%	35.5-44.9%
Platelet count	6-9 years	187-400 x 10  /L	187-400 x 10  /L
	10-13 years	177-381 x 10  /L	177-381 x 10  /L
	14-17 years	139-320 x 10  /L	158-362 x 10  /L
	Adults	135-317 x 10  /L	157-371 x 10  /L

We calculate the proportion of participants with laboratory abnormalities at weeks 2, 4, 8 and 10, and overall (i.e., a participant experienced a lab abnormality at any visit).

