5.2 PARTICIPANT EXCLUSION CRITERIA

- 1. Kidney or other solid organ or bone marrow transplant recipient
- 2. Allergy or intolerance to investigational agent
- 3. Secondary FSGS
- 4. Severe obesity, i.e., BMI >40 kg/m²
- 5. Live virus vaccine in the past 3 months
- 6. Malignancy, current or in the past 5 years
- 7. Active local or systemic bacterial, fungal or viral infection
- 8. Active or latent Hepatitis B, Hepatitis C, HIV, or tuberculosis defined as quantiferon test positive
- 9. History of demyelinating disease, e.g. Multiple Sclerosis or Guillain-Barre
- 10. History of heart failure
- 11. Active liver disease, defined as AST or ALT > 2.5x Upper Limit of Normal
- 12. Systemic lupus erythematosus or ANA > 1:80
- 13. History of inflammatory bowel disease, e.g. ulcerative colitis or Crohns disease
- 14. Cyclophosphamide in past 90 days, Rituximab in the past 180 days
- 15. Pregnancy or nursing

- 16. Blood white blood cell count <4,500/mm3; Hg <9 g/dL; Platelet count <150,000/mm3 at enrollment. Use of an erythropoiesis stimulating agent will not be an exclusion criterion.
- 17. Concurrent use of interleukin-1 antagonist (Anakinra), other TNF blocking agent, methotrexate or abatacept
- 18. Diabetic nephropathy

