## 8.2.3 Laboratory abnormality variables

Elevation of ALT, AST or total bilirubin of > 2x ULN were prespecified as events of interest and were coded as 1 for values  $\ge 2x$  ULN, 0 for values below 2 x ULN. These are calculated for each participant at each time point.

Abnormal low values for hemoglobin, hematocrit, and platelet count were specified as events of interest and were coded as 1 for values < age-matched LLN and 0 otherwise. Abnormal high values for hemoglobin, hematocrit, and platelet counter were also specified as events of interested and were coded 1 for values > age-matched ULN and 0 otherwise. Any laboratory abnormality for these laboratory parameters were coded as 1 if abnormally low or high and 0 otherwise. These are calculated for each participant at each time point.

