- Table 17. Proportion of participants achieving a nadir UPCR <1.5 g/g and at least a 40% reduction from baseline at week 10. As-Treated Population.
- Table 18.1. Proportion of Participants with Abnormal Laboratory Tests for ALT, AST, Total Bilirubin, Hemoglobin, Hematocrit, and Platelet Count Over the Course of the 10-Week Intervention Period. As-Treated Population.
- Table 18.2. Shift Table for Normal and Abnormal Laboratory Test Changes from Screening to Weeks 0, 2, 8, 10, and 14 in ALT, AST, Total Bilirubin, Hemoglobin, Hematocrit, and Platelet Count. As-Treated Population.
- Table 19. Correlations between TNF activation score and urinary MCP1/uCr and TIMP1/uCr biomarker levels at baseline. As-Treated Population with Kidney Biopsy Tissue Collected within 12 Months of Study Baseline.

- Table 20.1. Change from baseline to weeks 2, 4, and 8 in urinary MCP1/uCr. As-Treated Population.
- Table 20.2. Percent change from baseline to weeks 2, 4, 8, and 10 in urinary MCP1/uCr. As-Treated Population.
- Table 20.3. Urinary MCP1/uCr values at baseline and weeks 2, 4, 8, and 10. As-Treated Population.
- Table 21.1. Change from baseline to weeks 2, 4, and 8 in urinary TIMP1/uCr. As-Treated Population.
- Table 21.2. Percent change from baseline to weeks 2, 4, 8, and 10 in urinary TIMP1/uCr. As-Treated Population.
- Table 21.3. Urinary TIMP1/uCr values at baseline and weeks 2, 4, 8, and 10. As-Treated Population.
- Table 22. Change in uEGF/uCr levels from baseline to weeks 2, 4, 8, and 10. As-Treated Population.
- Table 23. Correlation coefficient between uEGF/uCr at baseline with changes and percent changes in urinary MCP1/uCr and urinary TIMP1/uCr biomarker levels and in eGFR and UPCR values at week 10. As-Treated Population.
- Table 24. Changes in FSGS-MCD Patient Reported Outcome (PRO) score from baseline to weeks 2, 4, 8 and 10. As-Treated Population.

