## 12.3 List of Figures

- Figure 1. CONSORT diagram. All Subjects.
- Figure 2.1. Spaghetti plot of changes from baseline to weeks 2, 4, 8, and 10 in urinary MCP1/uCr. As-Treated Population.
- Figure 2.2. Spaghetti plot of percent changes from baseline to weeks 2, 4, 8, and 10 in urinary MCP1/uCr. As-Treated Population.
- Figure 2.3. Spaghetti plot of urinary MCP1/uCr at baseline and weeks 0, 2, 4, 8, and 10. As-Treated Population.
- Figure 3.1. Spaghetti plot of changes from baseline to weeks 2, 4, 8, and 10 in urinary TIMP1/uCr. As-Treated Population.

- Figure 3.2. Spaghetti plot of percent changes from baseline to weeks 2, 4, 8, and 10 in urinary TIMP1/uCr. As-Treated Population.
- Figure 3.3. Spaghetti plot of urinary TIMP1/uCr at baseline and weeks 2, 4, 8, and 10. As-Treated Population.
- Figure 4.1. Spaghetti plot of changes from baseline to weeks 2, 4, 8, and 10 in eGFR. As-Treated Population.
- Figure 4.2. Spaghetti plot of percent changes from baseline to weeks 2, 4, 8, and 10 in eGFR. As-Treated Population.
- Figure 4.3. Spaghetti plot of eGFR at baseline and weeks 2, 4, 8, and 10. As-Treated Population.
- Figure 5.1. Spaghetti plot of changes from baseline to weeks 2, 4, 8, and 10 in UPCR. As-Treated Population.
- Figure 5.2. Spaghetti plot of percent changes from baseline to weeks 2, 4, 8, and 10 in UPCR. As-Treated Population.
- Figure 5.3. Spaghetti plot of UPCR at baseline and weeks 2, 4, 8, and 10. As-Treated Population.
- Figure 6.1. Spaghetti plot of participants with at least one abnormal laboratory value: ALT. As-Treated Population.
- Figure 6.2. Spaghetti plot of participants with at least one abnormal laboratory value: AST. As-Treated Population.
- Figure 6.3. Spaghetti plot of participants with at least one abnormal laboratory value: Total Bilirubin. As-Treated Population.
- Figure 6.4. Spaghetti plot of participants with at least one abnormal laboratory value: Hemoglobin. As-Treated Population.
- Figure 6.5. Spaghetti plot of participants with at least one abnormal laboratory value: Hematocrit. As-Treated Population.
- Figure 6.6. Spaghetti plot of participants with at least one abnormal laboratory value: Platelet Count. As-Treated Population.
- Figure 7.1. Scatterplot of TNF activation score and baseline urinary MCP1/uCr. As-Treated Population.
- Figure 7.2. Scatterplot of TNF activation score and baseline urinary TIMP1/uCr. As-Treated Population.

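### Table 18.1 does not separate laboratory abnormalities present before adalimumab from new ones, no listed table gives the proportion newly abnormal from the last pre-dose value, and post-dose white cells are in no listed laboratory output

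*SAP*

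**What the plan says.** **Endpoint.** Protocol 4.2.2 names the incidence of abnormal laboratory tests. SAP 4.2 item 4 makes this a proportion of participants for six tests: ALT, AST, total bilirubin, hemoglobin, hematocrit and platelets. Items 1 to 3 of the same list (adverse events) are defined as treatment-emergent. Edema, also in item 4, is analysed in SAP 9.2 and Table 14 as new or worsening against baseline.

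**Flags.** SAP 6.2.2: "We calculate the proportion of participants with laboratory abnormalities at weeks 2, 4, 8 and 10, and overall", where overall means abnormal at any visit. SAP 8.2.3 has low hemoglobin, hematocrit and platelets "coded as 1 for values < age-matched LLN and 0 otherwise", with a matching code for high values. For the liver tests it says "Elevation of ALT, AST or total bilirubin of > 2x ULN were prespecified as events of interest", then codes 1 at or above twice the limit and "0 for values below 2 x ULN". No flag refers to an earlier value.

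**Outputs.** The title of Table 18.1 ends "Platelet Count Over the Course of the 10-Week Intervention Period". Table 18.2 is a "Shift Table for Normal and Abnormal Laboratory Test Changes from Screening to Weeks 0, 2, 8, 10, and 14" for the same six tests. Figures 6.1 to 6.6 are of the type "Spaghetti plot of participants with at least one abnormal laboratory value: Platelet Count"; SAP 9.2 adds reference lines for the limits.

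**Entry.** Protocol 5.2 excludes "Blood white blood cell count <4,500/mm3; Hg <9 g/dL; Platelet count <150,000/mm3 at enrollment", and AST or ALT above 2.5 times an unspecified upper limit of normal (ULN).

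**White cells.** Protocol 7.1 puts the white cell count and differential in the complete blood count. Section 7.2.5 schedules that at screening and weeks 0, 2, 8 and 10, and at week 14 if the visit is in person. SAP 8.3 lists the white cell count as a baseline variable only.

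**The concern.** The proportion in Table 18.1 is a prevalence, whereas the protocol names an incidence. A participant who enters with low hemoglobin and does not change counts the same as one whose hemoglobin falls after the first dose. This is the only part of the SAP's safety endpoints that has no pre-dose condition in either its definition or its analysis. With at most 8 treated, one or two such participants move the figure a long way.

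White cells matter for a different reason. Protocol 2.3.1 names pancytopenia and cytopenia as risks of TNF blockers, and the white cell count is an entry criterion. Yet a reader of the listed laboratory outputs would never see a post-dose value.

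**Working it through.** **1. Can an eligible participant already be flagged?** Compare the lower limits of normal (LLN) in SAP 6.2.2 with the entry limits in Protocol 5.2 (hemoglobin from 9.0 g/dL, platelets from 150 x10^9/L).

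| Hemoglobin, age | LLN male / female | LLN minus 9.0, male / female |
|---|---|---|
| 6-8 | 11.5 / 11.5 | 2.5 / 2.5 |
| 9-10 | 11.8 / 11.8 | 2.8 / 2.8 |
| 11-14 | 12.4 / 11.9 | 3.4 / 2.9 |
| 15-17 | 13.3 / 11.9 | 4.3 / 2.9 |
| Adult | 13.2 / 11.6 | 4.2 / 2.6 |

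All 10 groups overlap.

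| Platelets, age | LLN male / female | LLN minus 150, male / female |
|---|---|---|
| 6-9 | 187 / 187 | 37 / 37 |
| 10-13 | 177 / 177 | 27 / 27 |
| 14-17 | 139 / 158 | none / 8 |
| Adult | 135 / 157 | none / 7 |

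Six of 8 groups overlap. There is no upper entry limit for platelets, so a high flag at entry is possible in all 8. Hematocrit and bilirubin have no entry limit.

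ALT and AST overlap between 2x and 2.5x ULN, provided eligibility uses the SAP's ULN. For ALT that is 2 x 55 = 110 to 2.5 x 55 = 137.5 U/L in males, and 90 to 112.5 in females. For AST from age 14 it is 96 to 120 and 86 to 107.5.

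**2. What this does to Table 18.1.** Let n be treated, k flagged at entry and still flagged, m newly flagged after dosing. Table 18.1 shows (k + m)/n; the newly abnormal proportion is m/(n - k). The values of k and m are assumed.

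| n | k | m | Table 18.1 | Newly abnormal |
|---|---|---|---|---|
| 8 | 2 | 0 | 2/8 = 25.0% | 0/6 = 0% |
| 8 | 0 | 2 | 2/8 = 25.0% | 2/8 = 25.0% |
| 8 | 2 | 1 | 3/8 = 37.5% | 1/6 = 16.7% |
| 6 | 2 | 1 | 3/6 = 50.0% | 1/4 = 25.0% |

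Each stable entry case adds 1/8 = 12.5, 1/7 = 14.3 or 1/6 = 16.7 points.

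**3. What Table 18.2 recovers.** It gives normal-to-abnormal counts at each visit, measured from screening. Protocol 7.2.1 allows screening up to 6 weeks before week 0. Someone who turns abnormal in that interval and stays so appears as a shift at weeks 2, 8 and 10 without having changed on drug.

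Assume 7 participants. Three are abnormal throughout and 4 are normal at screening, and Table 18.2 shows one normal-to-abnormal shift at each of weeks 0, 2, 8 and 10. Then 7 - 3 - 1 = 3 are normal at week 0.

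- If all four shifts are the same person, none of the 3 is newly abnormal after dosing.
- If they are four different people, all 3 are.

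So one set of shift counts fits 0, 1, 2 or 3 newly abnormal, with Table 18.1 overall (weeks 2 to 10) running from 4/7 (57.1%) to 6/7 (85.7%). Even when Table 18.1 reads 4/7, the answer may be 0 or 1 of 3.

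**4. White cells.** Tables 1 to 24, Listings 1 to 7 and Figures 1 to 12 in SAP section 12 were checked. White cells enter through the baseline table (Table 7) only. A post-dose fall would otherwise be visible only in the adverse event tables and listings, if it was reported as an event.

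**5. Internal contradictions.** A liver value exactly at 2x ULN is normal under SAP 6.2.2 (greater than) and abnormal under the 8.2.3 coding (at or above). SAP 6.2.2 asks for a week 4 proportion, but neither schedule (SAP 5.4, Protocol 7.2.5) has a week 4 visit, and Table 18.2 omits it.

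**The case against.** The strongest reply is that little information is lost for the six tests. Table 18.2 starts from a pre-dose value and shows week 0 as a column. Figures 6.1 to 6.6 draw every participant with any abnormal value, so anyone not drawn was never abnormal. With at most 8 people, and if the plots include the pre-dose visits, a reader can count the new cases by hand and see worsening in someone already low. The two 25% cases in step 2 would be told apart this way. Protocol 8.1.1 also lets a new or aggravated laboratory change be reported as an adverse event. Layouts are in a separate file, so this reading rests on titles and section text.

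Most of that stands. A reader might infer that the SAP gives no way to tell old from new; the documents do not support that. What remains is that a named secondary endpoint has to be rebuilt by eye, from plots, because no listed table states it from the last pre-dose value. The reply does not reach white cells, which have no plot or shift table.

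A reader might also infer that the SAP improperly narrowed the protocol by choosing six tests. Protocol 10.3.4 names no analytes and 10.1 leaves analysis detail to the SAP, so that charge is not supported. Nor can it be said that the adult bilirubin flag is undefined: the range as read stops at age 17, but the adult row may have been lost in reading the PDF.

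**Conclusion.** The point holds in this form. Table 18.1 mixes pre-existing and new abnormalities; Table 18.2 separates them visit by visit and from screening; the figures allow case-by-case reading; and no listed table gives the proportion normal at the last pre-dose value and abnormal at any post-dose visit. Post-dose white cell count and differential are collected but appear in no listed laboratory table or figure.

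The overlap between entry limits and flags is fixed by the documents for hemoglobin and platelets, and conditional on the ULN used at entry for ALT and AST. The size in practice is unknown, because the documents do not say how many participants enter already flagged; every k and m above is an assumption. It would therefore be wrong to infer that Table 18.1 will overstate toxicity by any particular amount. The endpoint is descriptive, and a single arm of 6 to 8 cannot establish attribution whichever way the table is built. The 2x ULN and week 4 contradictions need no assumption.

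**What to change.** 1. **Table 18.1.** Keep the current proportion and state that overall counts post-dose draws only. Add, per test, the number abnormal at week 2, 8 or 10 among those normal at week 0 (last pre-dose value if week 0 is missing), with that denominator shown.
2. **Table 18.2.** Use week 0 (last pre-dose value) as the reference in place of screening. Show low, normal and high for hemoglobin, hematocrit and platelets; SAP 8.2.3 already codes low and high.
3. **White cells.** Add white cell and neutrophil values, and change from week 0, by visit. Shown descriptively, they need no reference range.
4. **Coding.** Use one 2x ULN rule in SAP 6.2.2 and 8.2.3, and delete week 4 from 6.2.2. Check the source file for the adult bilirubin row, and act only if it is truly absent.
5. **Record** these changes in SAP section 10.

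No separate listing of worsening is needed, since Figures 6.1 to 6.6 largely show it.

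The cost is SAP wording and modest programming on data already collected; the flags are already computed at each time point. The downside is extra columns and newly abnormal denominators that may fall below 6 (4 in the last row of step 2), so counts should be shown beside any percentage.
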